9.1. Regulation Statement

This protocol has been developed and the study will be run in accordance with the ethical principles that have their origin in the Declaration of Helsinki (2013). Further, the study will be run in compliance with ISO 14155 (2nd ed.) 2011. Investigators will conduct this study in accordance with all applicable local or regional laws and regulations. Investigators will neither conduct procedures specific to the study nor collect subject data without prior approval or favorable opinion of any IEC under whose jurisdiction the conduct of this study falls. During the conduct of study activity, the investigators shall act in accordance with any further requirements as imposed by an IEC, IRB or other regulatory agency.

9.2. Informed Consent Procedure

Prior to the collection of any study specific data, the patient must complete the informed consent process and sign and date the informed consent form. The informed consent may be approved by an IEC, and is subject to local laws and regulations. Designated site staff will explain to the potential subject the study purpose, data to be collected and how it will be used, time and travel commitments and other expectations of a study subject. The patient will be given adequate time to consider participation in the study and review the informed consent form.

Any new information or protocol amendment that substantially alters the scientific validity of the study or affects the subjects' rights, safety, welfare, or their willingness to continue participation in the study, will result in re-consenting of currently active patients on an updated and approved ICF (as required by local law and regulation).

9.3. Protocol Amendments

If a protocol amendment substantially alters the scientific validity of the study or affects the subjects' rights, safety, welfare, or their willingness to continued participation in the study, then the subject should be re-consented on an updated and approved ICF(as required by local law and regulation). New procedures or processes which substantially alter the scientific validity of the study or affects the subjects' rights, safety, welfare, or their willingness to continued participation the study will not be implemented until an approval or favorable opinion has been granted by the reviewing IEC.

Appendix A – Study Schedule

Assessments			Post Treatment fol	ow-up ¹		Study Exit
	Screening	Injections ² (1\week for 2 weeks) and/or Splint (2 months)	1 Month	3 Month	6 Month	
Visit window			± 7 days	± 7 days	± 7 days	
Informed Consent	X					
Eligibility	X					
Demographics	X					
Radiographs	X					
Follow-up			X	X	X	
Medication Use	X	X	X	X	X	
DASH	X		X	X	X	
VAS		X ³	X	X	X	
Grip strength and Tip pinch strength test	X		X	X	X	
Kapandji Score and Nine-Hole Peg Test	X		X	X	X	
Adverse Events		□	□	□	□	□
Study Exit Form		□	□	□	□	X

1: Follow-up assessments may consist of a structured telephone interview, electronic self-report or, if standard of care, an office visit. 2: The first injection should take place within 28 days of completed screening. 3: Questionnaires should be obtained prior to injection procedure

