1.7. Study Objectives

The primary study objective is to determine whether two injections of OO and thumb splint are superior to the use of only the joint splinting in reducing pain.

1) The primary study endpoint is to establish the improvement in DASH score from baseline.

2) Secondary objectives of this study are:

- Improvement in VAS Pain,
- Improvement in Grip Strength Function,
- Improvement in Tip Pinch Function.
- Improvement in the Kapandji Score.
- Improvement in the Nine-Hole Peg Test.

2. Investigational Plan

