2.4.1.3. Confirm Eligibility

Screening assessments include:

- DASH questionnaire for index thumb joint
- X-Ray

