2.4.1.4. Baseline Recording

During the screening visit, the following information will be obtained and recorded in the subject study record and CRFs for all subjects.

- Signed and dated original ICF

- Inclusion and exclusion criteria
- Demographics
- Relevant Medical history, baseline conditions and medication use

The following baseline assessments will be completed prior to treatment and after final eligibility confirmation (during injection visit and prior to the injection procedure itself).

- VAS
- Grip strength test
- Tip pinch strength test
- Kapandji Score
- Nine-Hole Peg Test

All preoperative procedures are to be completed within 28 days prior to the injection procedure.

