2.4.6. Follow-up Visits

Follow-up assessment visits will be at the following intervals following the injection:

1 Month (\pm 7 days)

3 Month (\pm 7 days)

6 Month (\pm 7 days)

The following assessments and information will be collected at follow-up visits:

- DASH (all follow-up visits)
- VAS (all follow-up visits)
- Grip strength test (all follow-up visits)
- Tip pinch strength (all follow-up visits)
- Kapandji score (all follow-up visits)
- Nine-hole Peg test (all follow-up visits)
- Medication use (During the first 6-Month follow-up period, information on all medication usage will be collected)
- AEs (During the first 6-Month follow-up period, all AEs have to be reported.)

The study follow-up visits consist of a structured telephone interview and electronic self-report. The investigative center will contact the subject to complete the Follow-up, Adjunct Therapies and AE forms remotely.

Use of certain pain medication must be discontinued 48 hours prior to assessments (with the exception of aspirin taken for cardio protection). Aspirin in low dose would not be enough to affect any pain sensations. In addition, the low dose aspirin is supposed to be taken every day when taken for cardio-protection, so they should remain consistent on their regimen throughout the study. **In case of pain, it's possible to take Paracetamol 1000 mg 1 tablet (maximum dose 2 tablets per day).**

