2.6.4. Patient Reported Outcome Measures

- Disabilities of the Arm, Shoulder and Hand (DASH):

The DASH questionnaire is a tool already validated and used for the assessment of the patient's disability related to the pathology of the upper extremity (in this case of the hand) in the control of normal actions of daily life. The questionnaire consists of 38 questions, for a possible score ranging from the value 0 to the value 100. A higher score indicates the greater severity of the degree of disability felt by the patient in relation to the pathology.

- Visual Analogic Scale: The VAS is a validated measure of knee pain. The NRS is an 11-point Likert type scale anchored by 0 "no pain" and 10 "worst possible pain". Subjects rate their average pain over the last 48 hours.

- Grip strength test e tip pinch strength test:

The Grip Strength Test and the Tip Pinch Strength Test are designed to measure the maximum isometric force exerted by the muscles responsible for flexion of the metatarsals and phalanges, flexion of the fingers and adduction of the thumb. The tests are carried out by means of a dynamometer to record the changes in force in the gripping and gripper movements.

- Kapandji Score:

The Kapandji score assesses the patient's ability to oppose the thumb, assigning a score based on the point of the hand they can touch.

- Nine-Hole Peg Test:

The Nine-Hole Peg Test is a test that uses 9 pegs and a board with 9 holes: the patient is asked to place the pegs one by one in the holes and then remove them and put them back in the container. The score is given by the time in seconds that the patient takes to perform the maneuver.

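### The plan allows follow-up DASH and pain scores to be collected in different, unrecorded ways, possibly by an interviewer, and gives the pain scale two names

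*Combined protocol and SAP*

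**What the plan says.** The primary endpoint is a change in a patient-reported score (section 1.7): "The primary study endpoint is to establish the improvement in DASH score from baseline". Section 1.7 lists VAS pain as a secondary objective. Section 7.2 reports DASH and the NRS together as percentages of patients reaching 10.83 and 2 points.

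The mode of collection at follow-up is described twice:

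- Section 2.4.6: "The study follow-up visits consist of a structured telephone interview and electronic self-report". The centre then contacts the patient to "complete the Follow-up, Adjunct Therapies and AE forms remotely".
- Appendix A, footnote 1, attached to the follow-up column header that spans DASH and VAS: "Follow-up assessments may consist of a structured telephone interview, electronic self-report or, if standard of care, an office visit".

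The list in section 2.4.6 also requires hands-on tests each time, for example "Grip strength test (all follow-up visits)". Pinch strength, the Kapandji score and the peg test are listed in the same way.

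At baseline, section 2.4.1.3 lists the "DASH questionnaire for index thumb joint" among the screening assessments without saying how it is completed. Section 2.4.1.4 places baseline VAS "during injection visit and prior to the injection procedure itself".

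The pain instrument is introduced in section 2.6.4 as follows: "Visual Analogic Scale: The VAS is a validated measure of knee pain. The NRS is an 11-point Likert type scale". The anchors given there are 0 and 10.

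**The concern.** A change from baseline is easiest to interpret when the same instrument is given in the same way both times. Here a patient could answer alone on a screen at one visit and to a member of the centre's staff at another, and two patients could be handled differently at the same visit. A shift caused by the mode goes straight into the change score.

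The comparator is splint alone, so patients know what they received. No masking of the person who collects DASH is described. Scores given aloud to the treating centre are open to interviewer influence and to the wish to please, and a self-completed form avoids that addition.

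For pain there is a second gap. A marked line cannot be completed by telephone, whereas a 0-10 number can. With both names in use, the plan does not make clear that one instrument applies throughout. At stake are the precision and credibility of the primary endpoint, the pain endpoint and both responder percentages.

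**Working it through.** **1. The plan's own sample size.** Inputs from section 7.1: difference 1 SD, two-sided 5%, power 80%. n per group = 2 × (1.960 + 0.842)² / 1² = 15.7, so 16. Normal-approximation power at 16 is 80.7%. An exact t-test calculation gives 78.1% at 16 and needs 17. Enrolling 20 allows for 20% loss: 16 / 0.80 = 20. The stated figure reproduces. Section 7.1 makes no specific allowance for a mode effect.

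**2. The passages side by side.**

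| Item | Where | Mode |
|---|---|---|
| Follow-up, body text | 2.4.6 | Telephone and electronic; no office visit named |
| Follow-up, schedule | Appendix A, footnote 1 | Telephone, electronic or, conditionally, office visit |
| Forms done remotely | 2.4.6 | Three forms named; DASH and VAS not among them |
| Grip, pinch, Kapandji, peg test | 2.4.6, Appendix A | Every follow-up; need attendance in practice |
| Baseline DASH | 2.4.1.3, Appendix A | Screening; mode not stated |
| Baseline pain | 2.4.1.4, Appendix A footnote 3 | On site, before the injection |
| Analysis | 7.2 | t-test or Mann-Whitney; no term for mode |

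No section fixes the mode by patient or visit, requires the baseline mode to be repeated, or has the mode recorded. A change of mode is therefore permitted for pain and possible for DASH.

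**3. Cost if the mix of modes is the same in both arms.** The documents give no mode effect. Assume m = 0.2 to 0.5 SD of the analysed score and a 50/50 mix. The SD grows by √(1 + m² × 0.5 × 0.5), and the between-arm difference in means is unbiased.

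| m (SD) | SD factor | Power, 16 per group | Power, 20 per group |
|---|---|---|---|
| 0 | 1.000 | 80.7% | 88.5% |
| 0.2 | 1.005 | 80.4% | 88.2% |
| 0.3 | 1.011 | 79.9% | 87.8% |
| 0.5 | 1.031 | 78.3% | 86.6% |

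**4. What an imbalance between arms would do, if there were one.** Bias = m × gap, where the gap is the between-arm difference in the share of patients measured by one mode. The entries are the two-sided rejection probability with no true effect, 20 per group (noncentral t, noncentrality = bias × √(20/2)).

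| m (SD) | Gap 0 | Gap 25 points | Gap 50 points |
|---|---|---|---|
| 0.2 | 5.0% | 5.3% | 6.1% |
| 0.3 | 5.0% | 5.6% | 7.5% |
| 0.5 | 5.0% | 6.7% | 12.0% |

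With 16 per group the last column reads 5.9%, 7.0% and 10.5%. Both m and the gap are assumptions. With the same follow-up schedule in both arms, a gap of 0 is the natural starting point.

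**5. Responder percentages.** A shift common to both arms cancels from the difference in mean change, but it still moves individuals across a fixed threshold. If a change of mode shifted DASH by an assumed 3 to 5 points, that would be 3 / 10.83 = 28% to 5 / 10.83 = 46% of the responder threshold.

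**The case against.** The tempting stronger reading is that mode will track treatment: injected patients come to the clinic more often, so more of their scores are taken there and the primary comparison is confounded. The documents do not support this. Both arms have the same follow-up visits and assessments, and both receive splints for two months. The weekly injections run for two weeks, so they are over before the 1-month visit. Randomization is 1:1 and stratified by site (section 4.4.1), which largely balances site habits. This part of the objection stands.

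Three further inferences also go beyond the text:

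- **That DASH is read out by telephone.** Section 2.4.6 names three forms for remote completion and DASH is not one of them. Section 5.2 allows patients to complete CRFs. However, footnote 1 covers the DASH column and does allow an interview.
- **That the interviewer knows the allocation.** Section 4.4.1 limits the view of the allocation to an un-blinded research associate. The follow-up interviewer's knowledge is unspecified.
- **That sites will use a drawn line for pain.** Section 2.6.4 describes a 0-10 number. The inconsistent naming is documented, but use of two instruments is not.

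The strongest practical counter-argument is that the hands-on tests imply attendance at every visit, where DASH could simply be completed. That would reduce the problem. It also contradicts the remote wording, so the passages still need reconciling. Finally, patients' own knowledge of their treatment is probably the larger threat, and self-completion does not remove it.

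**Conclusion.** The point holds as a gap in how the primary and pain endpoints are measured. The two rules for follow-up mode differ, neither fits the in-person tests, and the plan permits mixed and possibly interviewer-administered collection without recording it. The change of mode from baseline is firm as a permitted event for pain and only possible for DASH.

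A reader might go on to infer a bias in favour of ozone on the primary endpoint. That does not follow: no text links mode to arm, and the size of any bias cannot be derived from the documents. If the mix is equal in both arms, the loss of power is small, at most 2.4 percentage points at 16 per group (80.7% − 78.3%) under the largest assumed mode effect. The error rates shown for unequal mixes are conditional illustrations. This is a cheap improvement worth making, and the sample size does not need to change.

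**What to change.** - Reconcile section 2.4.6 and Appendix A footnote 1 with the hands-on tests, stating whether patients attend at 1, 3 and 6 months.
- Have patients complete DASH and a single 0-10 numeric pain rating themselves, on an electronic form or on paper if needed. Do this in the same way at baseline and every follow-up, in both arms, before any contact with site staff on that occasion.
- Limit the telephone interview to the three forms that section 2.4.6 already names.
- Use one name for the pain scale in sections 1.7, 2.4, 2.6.4, 7.2, 7.4 and Appendix A. The 0-10 numeric rating is the natural choice because section 2.6.4 describes it and the 2-point threshold in section 7.2 refers to it.
- Record the mode on the CRF for any exception.

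The cost is wording changes and one CRF field, since electronic self-report is already planned. The sample size stays at 16 per group, 20 enrolled. The small downside is that some patients will need reminders or a paper form.

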Appendix B – Subject Procedure Flow
